Attachment A

Schedule of Events

Activity	Telephone Screen [-30 to -1 day]	CTSI Visit 1 [Day 0]	Week 1 [Days 1-7]	Week 2 [Days 8-15]	Week 3 [Days 16-23]	Week 4-11 [Days 24-80]	CTSI Visit 2 [Days 81-87]	Week 13 [Days 88-95]	Week 14 [Days 96-103]
Study team procedures									
Telephone Screen	X								
Schedule CTSI Visit	X					X (week 8)			
Study consent		X							
Anthropometric measurements & blood pressure		X					X		
Randomization					X				
Study intervention provided						X			
Participant intervention compliance check			X	X		X		X	X
Subject Survey		X	X	X		X	X	X	X
Continuous glucose monitoring			X					X	
Wrist accelerometer			X	X				X	X
Pulse oximetry			X (1 night, if needed)						
Final visit									optional
Laboratory Assessments									
HbA1c point of care fingerstick		X (if needed)							
Optional blood draw		X							

CONFIDENTIAL

This material is the property of the NYU School of Medicine and Langone Health. Do not disclose or use except as authorized in writing by the study sponsor
Drug/Device Template Version: 11 Jan 2019

## **1.1 Statistical Hypotheses**

Sleep intervention participants will have a lower percentage of time glucose is  $\geq 140\text{mg/dL}$  compared to control intervention participants after 8-weeks of treatment.

## **1.2 Analysis Datasets**

Primary analyses were performed within an intent-to-treat (ITT) sample, including all participants that were randomized to either the Sleep Intervention or Control Intervention.

## **1.3 Description of Statistical Methods**

### **1.3.1 General Approach**

The goal of this single site, parallel arm randomized clinical trial was to assess the impact of improved sleep on glycemic control (percent time glucose is  $\geq 140$ ) when compared to habitual sleep. Using descriptive analyses, the investigators described each variable using measures of central tendency (means, medians) and variability (standard deviations) for continuous variables; counts and percentages for categorical variables. Data were evaluated for anomalies (e.g., nonrandom missing data, erroneous outliers, multicollinearity, possible confounding) that may invalidate planned analyses.

### **1.3.2 Analysis of the Primary Efficacy Endpoint(s)**

A multivariable Linear regression model was used to assess the effect of the sleep intervention with the subject specific change in the percent time glucose is  $\geq 140$  (Time above target) from baseline as the continuous outcome variable and intervention arm (0=Control Intervention [CI], 1=Sleep Intervention [SI]) as a dichotomous predictor. Effect sizes were presented as beta coefficients and associated 95% confidence intervals, equal to the expected difference between the SI and CI. Important covariates that will be controlled for in these analyses include demographic characteristics including age (continuous), sex (female/male), and race (Asian, Black, White, Other). Statistical significance was determined with a  $p$ -value  $< 0.05$  using a two-tailed test for significance. Normality was assessed using a skewness cutoff of  $\pm 2$ , following established guidelines.

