Wearable sensor technology assessments will be as follows: pulse oximeter (baseline for 1 night, as needed); Wrist accelerometer (baseline and end of treatment 24/7 for 14 nights); Continuous glucose monitor (baseline and end of treatment 24/7 for 7 days).

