7.3.3 Intermediate Visits

7.3.3.1 At-home visits

Week 1 (Days 1 - 7)

- Record adverse events as reported by participant or observed by investigator.
- Participant will wear the continuous glucose monitor for 7 days 24/7. Return the continuous glucose monitor to the study team in the prepaid package after day 14.
- If needed, participant will wear the pulse oximeter for 1 night. Return the pulse oximeter to the study team in the prepaid package after 1 night of wear time.
- Record results of continuous glucose monitor and pulse oximeter.
- Participant will wear wrist accelerometer (24/7).
- Complete Sleep Diaries (daily), SRM-5 (daily), and Epworth Sleepiness Scale (day 6)
- Complete baseline surveys: ASA24 hour dietary recall; Composite Scale of Morningness; International Physical Activity Questionnaire; Pittsburgh Sleep Quality Index; PROMIS-Depression 6a; Sleep Environment Survey.
- Record participant's adherence to intervention program.

Week 2 (Days 8 - 14)

- Record adverse events as reported by participant or observed by investigator.
- Record results of wrist accelerometer.
- Complete Sleep Diaries (daily), SRM-5 (daily) and Epworth Sleepiness Scale (day 13).
- Record participant's adherence to intervention program.

Week 3 (Days 15-21)

- Participant to ship wrist accelerometer back to the study team in the prepaid package after 14 nights of wear time (day 15).
- Record adverse events as reported by participant or observed by investigator.
- Determine eligibility for intervention based on wrist accelerometry and pulse oximetry data.
- Randomize eligible participants to sleep intervention or control arm.
- Notify participant of eligibility and arrange for weekly videoconference intervention sessions.

Weeks 4-11 (Days 22 – 77)

- Record adverse events as reported by participant or observed by investigator.
- Record results of daily Sleep Diary and weekly Epworth Sleepiness Scale results.
- Administer the study intervention to the participant in accordance with the intervention manual for the sleep intervention arm or the control arm.
- Record participant's adherence to intervention program.

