Futility analysis. As this randomized clinical trial will also be used to provide preliminary data (e.g., effect sizes) for a future well-powered R01 application, we will not do a futility analysis.

9 Clinical Monitoring

Clinical site monitoring is conducted to ensure that the rights and well-being of human subjects are protected, that the reported trial data are accurate, complete, and verifiable, and that the conduct of the trial is in compliance with the currently approved protocol/amendment(s), with GCP, and with applicable regulatory requirement(s).

- The PI or project coordinator will audit one case per quarter, selected at random, to confirm compliance with IRB requirements, including conformance with informed consent requirements, verification of source documents, and investigator compliance.
- Authorized representatives of the IRB and the NINR may review de-identified information, as well as participants' identifiable information, for the purposes of assuring proper conduct of the research, addressing a specific reported incident, or verifying appropriate use of funds. The Quality Assurance and Quality Improvement Division of NYU's Research and Regulatory Services may audit the study to confirm compliance. Access of any protected health information will be done in the offices of the PI in his presence. No identifiable information may be copied or taken off-site.

10 Statistical Considerations

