10.4.2 Analysis of the Primary Efficacy Endpoint(s)

Linear regression models will be used to assess the effect of the sleep intervention with the subject specific change in the percent time glucose is ≥ 140 from baseline as the continuous outcome variable and intervention arm (0=Control Intervention, 1=Sleep Intervention) as a dichotomous predictor. Effect sizes will be presented as beta coefficients and associated 95% confidence intervals, equal to the expected difference between the SI and CI. Important covariates that will be controlled for in these analyses include demographic characteristics including age, sex, race/ethnicity and behaviors characteristics including diet quality and physical activity. The rationale for including these covariates is because of their associations with both sleep and glycemic control. Statistical significance will be determined with a p -value < 0.05 using a two-tailed test for significance.

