10.4.3 Analysis of the Secondary Endpoint(s)

The same analytic approach described in Section 10.4.2 will be used to assess the effect of the sleep intervention with the subject specific change in glucose variability.

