10.5 Sample Size

The primary analyses will involve comparing the mean change in the percent time glucose is ≥ 140 from baseline between the sleep intervention and control intervention arms. The study by Leproult et al⁷⁶ (N=16) reported no significant changes in insulin or glucose with sleep extension, but did not provide effect sizes for determining power; they did report large significant correlations ($\rho > 0.6$) between increased sleep time and insulin. Thus, for powering the current study, effect size assumptions come from previous research examining effects of weekend sleep extension on improvement in the calculated area under the glucose curve (Glucose AUC), which is similar to the primary endpoint we are studying here. Specifically, Killick et al⁷⁵ observed a mean improvement in Glucose AUC of 69.2 mmol min.L⁻¹ (SD = 57.7) associated with weekend sleep extension; this corresponds to an effect size of ~1.2 standard deviations. If we observe this large effect, we would need 20 subjects per arm to have 95% power in the current study, at an $\alpha = 0.05$. To protect against over-estimates in this observed effect, which was conducted in a study with <20 individuals and relied on a different sleep intervention than proposed here, we note that 74 individuals per arm would be required to maintain 95% power in the ITT analysis set for a 50% reduction in this effect (i.e., 0.6 SDs) at an alpha of 0.05; thus, we will recruit 75 subjects per arm in the current study. Under our expectation that at least 80% will achieve our PP definition (n=60 per arm), we would maintain power of at least 90% for this effect size in the PP analysis set. To maintain power for up to 20% loss to follow-up or non-adherence during the 8-week intervention, we will plan to enroll a total of 188 participants in the two arms.

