10.6 Measures to Minimize Bias

10.6.1 Enrollment/Randomization/Masking Procedures

After the 2-week at-home sleep assessment and baseline data collection, eligible participants will be randomly assigned to the sleep intervention group or to the time and attention matched control intervention group using a block randomization method. Selection bias will be reduced by using random block sizes and keeping the PI blind to the size of each block. Participants will be blinded to the group assignment. It will not be possible to blind the interventionists to the intervention. The study biostatistician will have no direct contact with study participants and will not be blinded to group assignment. The biostatistician will produce and maintain the randomization codes for the blocks. Randomization may only be unmasked by the biostatistician at the completion of analysis of the primary outcome, or for reporting of SAEs or UPs for which it will be essential to provide information to the PI on group assignment.

CONFIDENTIAL

This material is the property of the NYU School of Medicine and NYU Langone Health. Do not disclose or use except as authorized in writing by the study sponsor
Behavioral Intervention Template Version: 11 January 2019

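### The primary change-score model omits baseline % time ≥140, which is measured before randomisation; separately, the secondary and exploratory models inherit diet and activity covariates with no time point

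*SAP*

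**What the plan says.** SAP 1.3.2 fits a linear regression of the subject-specific change in % time ≥140 on arm. It describes the adjustment as: "Important covariates that will be controlled for in these analyses include demographic characteristics including age (continuous), sex (female/male), and race (Asian, Black, White, Other". Protocol 10.4.2 uses the same outcome and arm term with a longer list: "controlled for in these analyses include demographic characteristics including age, sex, race/ethnicity and behaviors characteristics including diet quality and physical activity". Neither list names baseline % time ≥140.

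The baseline value is available in time. Protocol 7.1.1 schedules "Continuous glucose monitor (baseline and end of treatment 24/7 for 7 days" and 7.3.3.1 places the baseline wear in week 1, without the as-needed qualifier given to pulse oximetry. Week 3 of the same section reads "Randomize eligible participants to sleep intervention or control arm", and 10.6.1 confirms the order: "After the 2-week at-home sleep assessment and baseline data collection, eligible participants will be randomly assigned".

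Protocol 10.4.6 allows adjustment for important covariates that turn out to be imbalanced. It names no variable.

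Protocol 10.4.3 applies the 10.4.2 approach to the secondary endpoint, "with the subject specific change in glucose variability", and 10.4.11 applies it to change in diet quality and physical activity. The SAP drops diet and activity for the primary endpoint. The SAP text available gives no secondary or exploratory model.

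**The concern.** **Primary model.** A change score subtracts the whole baseline value, which fixes its coefficient at 1. If the slope of follow-up on baseline differs from 1, change remains correlated with baseline, and that variation stays in the residual. Including baseline as a covariate removes it. The outcome already requires the baseline value, so nobody in the model would lack it. Precision matters here beyond the p-value, because section 8.8 says the trial "will also be used to provide preliminary data (e.g., effect sizes) for a future well-powered R01 application"; the estimate and its interval are themselves a product of the trial.

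**Secondary and exploratory models.** Diet and activity are measured both at baseline and at end of treatment (7.1.1), and 10.4.2 does not say which is the covariate. Section 2.1 describes both as routes by which sleep duration affects glycaemic control, so end-of-treatment or change values in the glucose-variability model could adjust away part of the effect. In 10.4.11 the same two variables are outcome and covariate at once. Two analysts following the text could obtain different estimates.

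**Working it through.** **1. The plan's own figure.** Protocol 10.5 takes 69.2/57.7 ≈ 1.2 SD from a weekend sleep-extension study and halves it to 0.6 SD: "we note that 74 individuals per arm would be required to maintain 95% power in the ITT analysis set". By noncentral t, two-sided 0.05, 74 per arm gives power 0.9521 and 73 gives 0.9496. The 74 reproduces. Inflation for 20% loss also holds: 75/0.8 = 93.75, so 94 per arm and 188 in total.

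**2. Planned model at 75 per arm.** There are seven parameters (intercept, arm, age, sex, three race terms), so residual df = 150 − 7 = 143. In units of the SD of change:

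- Half-width = t(0.975, 143) × √(2/75) = 1.977 × 0.1633 = 0.323.
- Power at 0.6 SD = 95.4%.

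**3. Adding baseline.** Residual df becomes 142. Let r be the baseline/follow-up correlation and k the follow-up SD divided by the baseline SD, both within age, sex and race. The documents give neither, so I assume r from 0.5 to 0.9 and k from 0.8 to 1.25.

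Variance ratio (with baseline ÷ without) = k²(1 − r²) / (1 + k² − 2rk). With k = 1 this is (1 + r)/2.

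| k = 1 | Variance ratio | 95% half-width | Power at 0.6 SD | n per arm for 95% power |
|---|---|---|---|---|
| Planned model | 1 | 0.323 | 95.4% | 74 |
| r = 0.5 | 0.75 | 0.280 | 98.8% | 56 |
| r = 0.7 | 0.85 | 0.298 | 97.7% | 63 |
| r = 0.9 | 0.95 | 0.315 | 96.3% | 70 |

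The extremes of the assumed range:

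- Largest gain, k = 0.8 and r = 0.5: 0.64 × 0.75 / (1.64 − 0.80) = 0.48/0.84 = 0.571. Half-width 0.244, power 99.8%; 1 − √0.571 = 24% narrower.
- No gain, k = 1.25 and r = 0.8: 1.5625 × 0.36 / (2.5625 − 2.00) = 0.5625/0.5625 = 1.000. Here rk = 1, so change is uncorrelated with baseline.

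On an even grid over the range the median variance ratio is 0.86 (1 − √0.86 = 7% narrower), and 22% of the grid lies above 0.95.

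**4. Simulation check.** Both models included age, sex and race, with demographics assumed to explain 10% of baseline variance; 6,000 trials per setting.

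| Setting | Power without baseline | Power with baseline |
|---|---|---|
| k = 1, r = 0.5 | 94.7% | 98.1% |
| k = 1, r = 0.7 | 94.7% | 97.1% |
| k = 1, r = 0.9 | 94.9% | 95.5% |
| k = 0.8, r = 0.5 | 94.9% | 99.7% |
| k = 1.25, r = 0.8 | 95.2% | 95.2% |

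In the last setting the mean standard error was 0.1657 without baseline and 0.1662 with it, a rise of 0.3%. Type I error was 4.7% to 5.2% across settings for both models.

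**5. Diet or activity as both outcome and covariate (10.4.11).** Take k = 1 and a true effect of 0.6 SD. Within arm, the slope of change on the end-of-treatment value is 1 − r. Adjusting for that value leaves an expected estimate of 0.6 − (1 − r) × 0.6 = r × 0.6.

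| r | Expected, end-of-treatment covariate | Simulated estimate (power) | Simulated, baseline covariate (power) |
|---|---|---|---|
| 0.5 | 0.30 | 0.300 (52%) | 0.600 (99%) |
| 0.7 | 0.42 | 0.418 (76%) | 0.595 (98%) |
| 0.9 | 0.54 | 0.542 (92%) | 0.602 (96%) |

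**The case against.** The case against runs as follows.

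- **The planned analysis is legitimate.** It matches the mean-change comparison in 10.5 and has about 95% power at the design effect. This stands: the point concerns efficiency, not validity.
- **The gain cannot be verified.** r and k are not in the documents, and the grid median describes a chosen range, not this trial. This also stands. The 24% is a corner of the range, and the gain may be nil. The simulated powers with baseline run slightly below the formula values, because the formula ignores chance correlation between arm and covariates. Starting the range at r = 0.3 would enlarge the gain (variance ratio 0.65 at k = 1). The trade remains lopsided: up to 24% narrower against about 0.3% on the standard error in the worst setting simulated.
- **The plan may already cover it.** The SAP list is introduced by a word that need not be exhaustive, and 10.4.6 could reach baseline % time ≥140. If the list is open, the primary model is not fully specified. The 10.4.6 rule operates only after an imbalance is seen, so the model would depend on the data.
- **The diet and activity point rests on overview text.** Protocol 10.1 defers to the SAP, whose available text ends at the primary endpoint. The reason 10.4.2 gives for these covariates, association with both sleep and glycaemic control, fits baseline values. This largely stands. The figures in step 5 are the worst reading of an ambiguity, and they concern exploratory endpoints.

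**Conclusion.** The concern holds. Baseline % time ≥140 belongs in the primary model: it is scheduled for everyone before randomisation, loses no participants and costs one degree of freedom. Under the assumed r of 0.5 to 0.9 and k of 0.8 to 1.25, the interval narrows by 0% to 24%. With equal SDs, power at 0.6 SD rises from 95.4% to between 96.3% and 98.8%, a modest gain at the planned effect. The planned estimate, its type I error and the sample size are all sound.

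The missing time point for diet and activity is a lesser matter. It biases nothing if baseline values are used, and whether SAP text not available here settles it cannot be determined. As the protocol stands, the wording permits a reading that would shrink an exploratory effect to r times its true size.

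This is a change that should be made, but it does not threaten the validity of the primary conclusion.

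**What to change.** **If the analysis has not been run:**

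- SAP 1.3.2 and protocol 10.4.2: regress change in % time ≥140 on arm, baseline % time ≥140 (continuous), age, sex and race. Delete diet quality and physical activity from 10.4.2 so that it agrees with the SAP.
- Protocol 10.4.3 and 10.4.11: state the model as change in the outcome on arm, the baseline value of that outcome, age, sex and race. Add that no diet or activity value measured after randomisation is a covariate.
- Protocol 10.4.6: replace the imbalance-triggered adjustment with this fixed list.

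**If it has been run,** as the past tense in SAP 1.2 and 1.3.2 suggests: keep the SAP model as primary, report the baseline-adjusted model as a labelled sensitivity analysis, and add one sentence giving the covariates and time points used in the secondary and exploratory models.

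The cost is wording in five sections in the first case, or one extra model and one sentence in the second. Neither needs new data.
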